1. SYNOPSIS

Study Title	Impact of price promotions on purchases of confectionery and snacks: a randomised controlled trial in an experimental online supermarket study	
Internal ref. no.	N/A	
Study Design	Randomised controlled trial	
Study Participants	Healthy volunteers from the UK	
Planned Sample Size	500	
Planned Study Period	June – December 2021	
	Objectives	Outcome Measures
Primary	To investigate the effect of promotions on the total number of calories selected	Difference in the absolute energy (kcal) of the final basket between the two groups
Secondary	
To investigate the effect of promotions on the nutritional content of the items selected overall, and across the individual target food categories
 
To explore the impact of removing promotions by socioeconomic status
	
Difference in the absolute sugar (g, kcal, %E), salt (g), and saturated fat (g, kcal, %E) of the final basket between the two groups
 
Difference in the absolute energy (kcal), sugar (g, kcal, %E), salt (g), and saturated fat (g, kcal, %E) between the two groups across the individual target food categories
 
Analyses of the primary and secondary outcomes specified above by gender, age group, ethnic group (White vs Non-White), BMI stratified into <30 and ≥ 30kg/m² groups, education level (lower vs. higher), and household income (lower vs. higher)

Exploratory	To investigate the acceptability of the intervention	Rating scores and open-ended answers from the follow-up questionnaire

2. ABBREVIATIONS

CI	Chief Investigator
CLARHC	Collaboration for Leadership in Applied Health Research and Care
IDREC	Interdisciplinary Research Ethics Committee
SAP	Statistical Analysis Plan
SFA	Saturated Fat
TPR	Temporary Price Reduction

3. BACKGROUND AND RATIONALE

As a nation we eat more energy, free sugars, saturated fat and salt than recommended for good health (1). These nutrients contribute to the burden of major chronic diseases, including cardiovascular disease and diabetes, principally through effects on blood cholesterol, blood pressure, insulin sensitivity or body weight (2-6). In addition, persistent inequalities in dietary intake underpin inequalities in long-term health outcomes. Despite decades of health promotion, dietary change is slow. Growing evidence suggests people need more than general knowledge about the healthfulness of foods to change behaviour (7-11).

Food purchasing is a key antecedent of food consumption and interventions to change food purchasing habits may be more impactful than interventions intended to change consumption at the moment of eating. Supermarkets account for the majority of the weekly expenditure on food and drinks, estimated to be around 87% of all UK retail grocery sales (12). Impactful, scalable and sustainable approaches within supermarkets are particularly needed in order to shift population-level intakes to be closer to the recommendations for calories, sugar, salt and saturated fat.

Previous systematic reviews of supermarket interventions have identified effective strategies to support dietary change (13-23). Evidence is generally stronger for economic (e.g. price interventions or price promotions), positioning and availability interventions. However, many of the interventions described in the literature are multi-component, and there is a challenge in attributing their effectiveness to any single strategy. In the 2020 Obesity Plan, the government in England laid out plans to introduce legislation to restrict the promotion of high fat salt sugar (HFSS) foods, by restricting volume promotions such as 'Buy One Get One Free'. This is based on observational evidence of purchasing habits. Specific evidence of the impact of removing promotions is of interest to policymakers and could help in shaping effective but proportionate policies.

Online supermarkets offer unique opportunities to deliver and support complex nutrition interventions that can often be tested and scaled up more rapidly and feasibly using digital technology than in-store interventions. There is some evidence that baseline purchases made online tend to be healthier than purchases in physical stores, but less is known about the effectiveness of interventions delivered online to change behaviour.

The purpose of this project is to test the effectiveness of the removal of price promotions on confectionery and snacks on the energy, sugar and saturated fat content of items selected while shopping online in a representative sample of UK adults. The proposed intervention can be easily implemented, and could reach large numbers of people, meaning that if it is effective it could have a significant population impact and be very cost-effective, even if the effect size is smaller than more intensive interventions.

4. OBJECTIVES AND OUTCOME MEASURES

	Objectives	Outcome Measures
Primary	To investigate the effect of promotions on the total number of calories selected	Difference in the absolute energy (kcal) of the final basket between the two groups
Secondary	
To investigate the effect of promotions on the nutritional content of the items selected overall, and across the individual target food categories
 
To explore the impact of removing promotions by socioeconomic status
	
Difference in the absolute sugar (g, kcal, %E), salt (g), and saturated fat (g, kcal, %E) of the final basket between the two groups
 
Difference in the absolute energy (kcal), sugar (g, kcal, %E), salt (g), and saturated fat (g, kcal, %E) between the two groups across the individual target food categories
 
Analyses of the primary and secondary outcomes specified above by gender, age group, ethnic group (White vs Non-White), BMI stratified into <30 and $\geq 30 \text{ kg/m}^2$ groups, education level (lower vs. higher), and household income (lower vs. higher)

Exploratory	To investigate the acceptability of the intervention	Rating scores and open-ended answers from the follow-up questionnaire

5. STUDY DESIGN

This is a randomised controlled trial with a parallel design. We will use an experimental online shopping platform to mimic the experience of online grocery shopping. Each participant will be randomised 1:1 to one of two groups and will participate in an online shopping task for about 10 minutes during which they will be exposed to a selection of products including promotions or with no promotions. We will collect and analyse data from the online platform on food selection during the task.

6. INTERVENTION

This study uses a bespoke virtual online supermarket shopping (OLS) platform, hosted by The University of Oxford, which emulates a real online supermarket for research purposes relating to food purchasing interventions (www.woodssupermarket.co.uk). The site is populated with approximately 23,000 current supermarket products drawn from foodDB (April 2019), a weekly updated database of food and drinks available for purchase in six UK online supermarkets (24).

Participants will be asked to imagine they are buying snacks for a night in with 4 friends, with a maximum limit of £10. They will be asked to select products from the following categories, which are aligned and named in the way items are presented in the store:

- Confectionery
- Biscuits and crackers
- Crisps, nuts and snacking fruit
- Cakes and tarts

The shopping task is estimated to take participants 10 minutes to complete. Participants will only be asked to complete the shopping task once. Participants will be provided with the following instructions:

“We would like you to do some online grocery shopping on a supermarket website. This is not a real supermarket, and you will not be asked to spend your own money.

We would like you to imagine you are buying snacks for a night in with 4 friends, up to a limit of £10. You should select products from the following categories:

- *Confectionery*
- *Biscuits and crackers*
- *Crisps, nuts and snacking fruit*
- *Cakes and tarts*

We would ask you not to select any additional items from your usual shopping list.

When doing your shopping, try to imagine you are doing your own grocery shopping and choose foods that you and your friends would eat. You should choose the things you normally buy or wouldn't mind eating.

To make sure you get your reward, please make sure you buy at least £5 worth of products within the suggested food categories”

Participants will be randomly allocated to one of the two following groups when shopping online:

1. Promotions removed: No promotions present on any of the products within the target food categories [confectionery; biscuits and crackers; crisps, nuts and snacking fruit; cakes and tarts] offered to participants when searching for products.
2. Promotions included: Participants in this group will see a version of the website which will reproduce the types and frequency of promotions that can be found in any online supermarket, for example multi-buy offers and temporary price reductions will be applied to a pre-determined percentage of food products within the target categories [confectionery; biscuits and crackers; crisps, nuts and snacking fruit; cakes and tarts]. Promotions will be applied to match the current levels and types of promotions on the website of the largest UK retailer present in a specific week, shortly before the study launch.

7. PARTICIPANT IDENTIFICATION AND RECRUITMENT

7.1. Study Participants

Eligible participants will be UK adults who are responsible for a substantial proportion of their household grocery shopping, able to read and understand the instructions provided and able to provide online consent to take part in the study. Participants will be required to have access to a computer and the internet.

People who are following a vegan, gluten-free, dairy-free or sugar-free diet will not be eligible to participate to minimise the risk of unbalancing the groups with people choosing from a restricted selection of products.

7.2. Inclusion Criteria

- UK adults, aged ≥ 18 years.
- Able to speak and read English.
- Willing and able to give informed consent for participation in the study.
- Having access to a computer and Internet.

7.3. Exclusion Criteria

The participant may not enter the study if ANY of the following apply:

- They are following a dairy-free or sugar-free diet.

8. STUDY PROCEDURES

8.1. Recruitment

Participants will be recruited from the volunteer panel Prolific Academic (<https://www.prolific.co>).

8.2. Screening and Eligibility Assessment

Panel members will be sent an email introducing the study and including a link to the participant information sheet. Panel members who are interested in taking part in the study will be asked to click on a web-link from the email, which will take them to the study registration website (on Qualtrics). At this registration website, they will be asked screening questions indicating their responsibility for shopping, if they have any dietary restriction, if they regularly buy products from the target categories for their household, and to confirm their age and country of residence. They will also be able to re-read the detailed participant information before consenting to participate.

8.3. Informed Consent

After reading the detailed participant information sheet and answering screening questions to confirm they meet the inclusion/exclusion criteria; and if they are happy to proceed, participants will be asked to give consent electronically to take part in the study.

Written electronic versions of the Participant Information and Informed Consent will be presented to the participants detailing no less than: the exact nature of the study, what it will involve for the participant and the implications and constraints of the protocol. It will be clearly stated that the participant is free to withdraw from the study at any time for any reason and with no obligation to give the reason for withdrawal. The participant will be allowed as much time as wished to consider the information. Electronic Informed Consent will then be obtained by means of clicking on a tick box.

8.4. Randomisation

Randomisation will be performed by the survey platform Qualtrics via computerised random number generation on a 1:1 basis with random block sizes and participants will be directed to a website that introduces an online shopping task. Allocation concealment is achieved, as participants are recruited from independent research panels and are being directed by automatic randomisation in the survey platform. Details of the intervention are described in Section 6.

8.5. Blinding

Investigators will be blinded to intervention allocation and will not be able to manipulate any study parameter following the initial study set up, as all study procedures are taking part in the online platform. The outcome assessment is blinded, as it happens automatically in the online platform. The statistician who will analyse the data will be blinded to intervention allocation. Participants will only be aware of the trial arm that they are exposed to and will be unaware of the other trial arm.

8.6. Baseline Assessments

Following consent and completion of the shopping task, participants will complete a baseline questionnaire on demographic, shopping, and health data (Appendix B).

8.7. Follow-up

Participants will complete a short post-intervention survey (Appendix B) about the acceptability of the intervention in the online shopping task and their usual shopping behaviours.

8.8. Discontinuation/Withdrawal of Participants from Study

Each participant has the right to withdraw from the study at any time. Participants will not be replaced as we will recruit sufficient sample size to allow for non-completion rate. Withdrawal from the study, based on the pre-defined completion criteria (section 9.2), will result in exclusion of the data for that participant from analysis.

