9. STATISTICS AND ANALYSIS

9.1. The Number of Participants

There are no previously reported standard deviations of the mean difference from similar trials (e.g. where a one-off shop is done) to guide the estimation of the effect size and standard deviation, and, thus, the calculation of the sample size. However, the study by Brimblecombe *et al.* (25) implemented a complex intervention within real supermarkets in Australia where promotions on high sugar products were removed, including confectionery and sugary drinks. This study found a total reduction of -22% in sales (g/MJ) in confectionery, a difference of -4.5% (SD 15) compared to control; and a reduction of -8% in sugar-sweetened soft drinks, a difference of -13% compared to control.

A total sample of 500 participants (250 in each group) would be needed to detect a minimum effect size of -4.5% in total kcal from the target categories, with 90% power, 5% alpha and 10% attrition.

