9.2. Analysis of Outcome Measures

Completion of the task will be defined as spending at least £5 on products from the target categories.

Primary Analysis

Linear regression models will compare the total energy (kcal) purchased in the two groups. Any baseline variables (e.g. demographic characteristics) which appear to have been imbalanced between groups will be adjusted in the model.

Secondary Analysis

Linear regression models will compare the (i) total sugar (g, kcal, %E), (ii) total salt (g, kcal, %E) and (iii) total SFA (g, kcal, %E) purchased in the two groups.

Secondary analyses will also compare differences in total energy (kcal), total sugar (g, kcal, %E), total salt (g, kcal, %E) and total SFA (g, kcal, %E) across the individual target categories.

We will also conduct secondary analyses of the primary and secondary outcomes specified above by gender, age group, ethnic group (White vs Non-White), BMI stratified into <30 and ≥ 30 kg/m² groups, education level (lower vs. higher), and household income (lower vs. higher) provided we have sufficient numbers within each subgroup ($n \geq 30$).

Descriptive analysis

The exploratory outcome measures will be discussed descriptively.

A Statistical Analysis Plan will be finalised before conducting the statistical analysis.

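### Section 9.1's 500 participants give about 89% power, not 90%, at the stated 10% attrition if the printed SD of 15 and a two-sided test were used: a minor discrepancy that section 8.8 inherits

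*Combined protocol and SAP*

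**What the plan says.** Protocol section 9.1 states that "A total sample of 500 participants (250 in each group) would be needed to detect a minimum effect size of -4.5" per cent in total kcal, "with 90% power, 5% alpha and 10% attrition". The attrition is thus one of the conditions that the 500 is meant to satisfy. The only SD in that section belongs to a cited store trial's confectionery result, "a difference of -4.5% (SD 15) compared to control". The section does not say outright that 15 was the planning SD, and it does not say whether the 5% is one-sided or two-sided.

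The design is a simple two-group comparison: "Each participant will be randomised 1:1 to one of two groups" (section 5) and "Linear regression models will compare the total energy (kcal) purchased in the two groups" (section 9.2). Completion means spending at least £5 in the target categories (section 9.2). Under section 8.8, withdrawal judged by that criterion "will result in exclusion of the data for that participant from analysis", and "Participants will not be replaced as we will recruit sufficient sample size to allow for non-completion rate". The synopsis and the SAP summary also give 500. Nothing in either document provides for recruiting more.

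**The concern.** Non-completers are dropped from the analysis and not replaced, so each one reduces the analysed sample directly. The allowance built into the 500 is therefore all that protects the stated power. If it covers less than the stated 10%, then 500 randomised, 10% loss and 90% power do not quite agree on the printed inputs. Someone using the 90% figure to interpret a null result would be relying on slightly more power than those inputs give. The issue here is only the attrition allowance. Whether an SD from store sales suits a one-off basket of kcal is a separate question.

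**Working it through.** **Inputs.** From section 9.1: difference 4.5 and SD 15 (both in percentage points), power 90%, alpha 5%, attrition 10%, total 500 (250 per arm). From section 5: 1:1 allocation. Assumed: SD 15 is the planning SD, and the test is two-sided.

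**1. Trying to reproduce 500.** The standardised difference is 4.5/15 = 0.30. By the normal approximation,

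n per arm = 2 × (1.960 + 1.282)² / 0.30² = 2 × 10.507 / 0.09 = 233.5, so 234 (468 in total).

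The t distribution gives 234.5, so 235 (470 in total).

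Inflating for 10% loss, with the arms kept equal:

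| Basis | Analysed | Divided by 0.9 | Multiplied by 1.1 |
|---|---|---|---|
| Normal, two-sided | 468 | 520 | 516 |
| t, two-sided | 470 | 524 | 518 |
| Normal, one-sided 5% | 382 | 426 | 422 |

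None of these gives 500. The nearest is 516.

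**2. What 500 delivers.** With 10% lost, 500 × 0.9 = 450 are analysed, or 225 per arm.

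Power (normal) = Φ(0.30 × √(225/2) − 1.960) = Φ(3.182 − 1.960) = Φ(1.222) = 88.9%.

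The t distribution gives 88.8%. With all 500 analysed, power is 91.8% (normal) or 91.7% (t).

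**3. Detectable difference at 90% power with 225 per arm.** 3.2415 × 15 × √(2/225) = 4.58 (normal), or 4.59 (t).

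**4. Loss that 500 can absorb at 90% power.** 1 − 468/500 = 6.4% (normal), or 1 − 470/500 = 6.0% (t).

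**5. Sensitivity to rounding of the SD.** The SD is printed as a whole number. With the difference held at 4.5, t distribution, 10% loss and equal analysed arms:

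| SD | Analysed for 90% | Divided by 0.9, rounded | Power at 225 per arm |
|---|---|---|---|
| 14.5 | 440 | 489 | 90.7% |
| 14.65 | 448 | 498 | 90.2% |
| 14.7 | 452 | 502 | 89.97% |
| 15 | 470 | 522 (524 with equal arms randomised) | 88.8% |
| 15.49 | 500 | 556 | 86.8% |

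All five SDs print as 15. An SD of about 14.65 to 14.7 would reproduce 500.

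**The case against.** The strongest objection is the rounding. The SDs that print as 15 imply totals from about 489 to 556, and 500 lies inside that range. A reader might infer that the protocol's figures cannot be reconciled. They do not show that, because an unrounded SD near 14.7 would reconcile them. What stands is that no such SD is printed, so the sample size cannot be reproduced from the document.

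Second, two inputs are readings. Section 9.1 says that similar trials have reported no SD, and then quotes 15 from another setting. It also leaves sidedness open. With a one-sided 5% test, 450 analysed would give about 94% power. However, 15 is the only SD given and it accompanies exactly the 4.5 used as the design difference. No one-sided test is stated, and that reading does not give 500 either.

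Third, the primary regression may adjust for baseline variables. If these explained about 4.3% of the variance (an assumption), power with 450 analysed would be back to 90.1%. That is possible, but section 9.1 does not count on it, and adjustment is planned only for variables that look imbalanced.

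Fourth, a reader might conclude that section 8.8's reason for not replacing participants is false. The text does not support that. Section 8.8 names neither a rate nor a power, and 500 does contain an allowance of 30 to 32 participants above the 468 to 470 needed. It falls short only of the 10% stated in section 9.1.

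**Conclusion.** The point holds as a minor discrepancy in section 9.1, which section 8.8 inherits. It assumes that SD 15 is the planning value, that the test is two-sided and that 500 counts those randomised. On that basis the stated total is 20 to 24 below what 90% power at 10% loss requires. Power at 10% loss is about 89%, a shortfall of about 1.1 to 1.2 percentage points, and the real tolerance for non-completion at 90% power is about 6%.

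It would be tempting to call the trial underpowered or to ask for more enrolment. The figures support neither: 89% power and a detectable difference of 4.6 against 4.5 make no practical difference to the design. What needs correcting is the statement.

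**What to change.** In section 9.1, state the SD and the sidedness used, and restate the result. For example: assuming SD 15 and a two-sided 5% test, 500 randomised without replacement gives about 89% power at 10% non-completion (450 analysed), or 90% if non-completion does not exceed about 6% (470 analysed). If an unrounded SD near 14.7 was used, print it; the 90% figure can then stay. Giving the assumptions alongside the numbers matters, because both the 89% and the 6% depend on them.

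In section 8.8, refer to the restated figure in section 9.1. The no-replacement rule and the target of 500 can stay as they are.

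The cost is wording only. The SAP summary already describes the shopping task in the past tense, and this change affects neither conduct nor analysis. If SD 15 is confirmed, the stated power becomes slightly less favourable.

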8.9. Definition of End of Study

The end of study is the completion of the baseline questionnaire and post-intervention survey following the shopping task.

9. STATISTICS AND ANALYSIS

9.1. The Number of Participants

There are no previously reported standard deviations of the mean difference from similar trials (e.g. where a one-off shop is done) to guide the estimation of the effect size and standard deviation, and, thus, the calculation of the sample size. However, the study by Brimblecombe *et al.* (25) implemented a complex intervention within real supermarkets in Australia where promotions on high sugar products were removed, including confectionery and sugary drinks. This study found a total reduction of -22% in sales (g/MJ) in confectionery, a difference of -4.5% (SD 15) compared to control; and a reduction of -8% in sugar-sweetened soft drinks, a difference of -13% compared to control.

A total sample of 500 participants (250 in each group) would be needed to detect a minimum effect size of -4.5% in total kcal from the target categories, with 90% power, 5% alpha and 10% attrition.

